4. STATISTICAL ANALYSES

4.1. General Considerations

All data collected in this study will be presented separately by disease cohort using summary tables, figures, and data listings. All analyses will be performed using Statistical Analysis Software[®] (SAS[®]) release, version 9.4 or higher (SAS Institute Inc., Cary, NC, USA) or other validated statistical software.

All efficacy and safety analyses will be summarized separately for the 26-week Blinded Initial Evaluation Period, 24-week Blinded Extended Treatment Period, and 2-year OLE Period.

The analyses for participants in the LN cohort and IgAN cohort will be conducted and reported separately.

The primary comparison will be on the ALXN2050 180 mg treatment group versus the placebo treatment group. A smaller number of participants randomized to the ALXN2050 120 mg treatment group will be used for supportive data and will be summarized descriptively only with no formal statistical comparisons planned. As supplemental analyses, the comparisons will be carried out on the ALXN2050 Total treatment group (ALXN2050 180 mg and ALXN2050 120 mg) versus the placebo treatment group.

For the IgAN cohort, participants initially randomized to the placebo treatment group will receive ALXN2050 in the 24-week Blinded Extended Treatment Period. Therefore, analysis of the secondary endpoints during the 24-week Blinded Extended Treatment Period (Weeks 26 through 50) will be summarized separately for each treatment group assigned during the 26-week Blinded Initial Evaluation Period (Baseline through Week 26). During the 24-week Blinded Extended Treatment Period, baseline for the placebo treatment group will be redefined as the last measurement taken before the first dose of ALXN2050 during the 24-week Blinded Extended Treatment Period (ie, the Week 26 measurement).

The applied methods for statistical descriptive analyses and presentations will be based on the types of variables being tested.

- 1. Overall summary of descriptive statistics for continuous variables will include number of observations, mean, standard deviation (SD), median, minimum, and maximum, interquartile range (IQR), first quartile, and third quartile values in each treatment group. Observed difference will be summarized in a 2-sided 90% confidence interval (CI).
- 2. Overall summary of descriptive statistics for categorical variables will include frequency counts, percentage of participants, and 2-sided 95% CI of point estimate based on exact confidence limits using the Clopper-Pearson method.

Summaries of study and participant characteristics (eg, disposition, demographics and baseline characteristics, medical history, and protocol deviations) are described in Section 6.2.

4.1.1. Data Presentation for the 26-Week Blinded Initial Evaluation Period

Data summaries for the 26-week Blinded Initial Evaluation Period will be presented by randomized treatment group (ie, "ALXN2050 180 mg", "ALXN2050 120 mg", "ALXN2050 Total" and "Placebo") and total when applicable. All assessments for Week 26 will be performed prior to dosing. Dosing on Week 26 will be considered the start of the 24-week Blinded Extended Treatment Period.

4.1.2. Data Presentation for the 24-Week Blinded Extension Treatment Period

For the LN cohort, data summaries for the 24-week Blinded Extension Treatment Period will be presented by randomized treatment group and total when applicable.

For the IgAN cohort, summaries will be presented by treatment sequence (ie, "ALXN2050 180 mg", "ALXN2050 120 mg" and "Placebo to ALXN2050 180 mg" or "Placebo to ALXN2050 120 mg"). ALXN2050 Total, which consists of all the participants who were treated with ALXN2050 during the 24-week Blinded Extended Treatment Period, will be added when applicable. "ALXN2050 120 mg & 180 mg" which consists of participants who initially randomized to ALXN2050, will be included in efficacy tables when applicable. In addition, the baseline for the IgAN cohort will be defined as the originally randomized baseline and re-baseline will be defined as the last measurement collected prior to Week 26.

4.1.3. Data Presentation for the 2-Year OLE Period

For the LN cohort, data summaries for the OLE Period will be presented by treatment sequence if the optimal dose is identified at Week 26 (ie, "ALXN2050 180 mg to optimal dose", "ALXN2050 120 mg to optimal dose" and "Placebo to allowed concomitant therapy only"). The optimal dose presented here can be replaced with the actual identified dose based on the results of the Week 26 primary analysis.

For the IgAN cohort, summaries will also be presented by treatment sequence (ie, "ALXN2050 180 mg to optimal dose", "ALXN2050 120 mg to optimal dose" and "Placebo to ALXN2050 180 mg to optimal dose", "Placebo to ALXN2050 120 mg to optimal dose"). ALXN2050 Total, which consists of all the participants who treated with ALXN2050 during this period, will be added when applicable.

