8.3.1. Time Period and Frequency for Collecting AE and SAE Information

All AEs and SAEs will be collected from the signing of the ICF until the Safety Follow-up Visit.

All SAEs will be recorded and reported to Alexion immediately and under no circumstance should this exceed 24 hours, as indicated in Section 10.3. The Investigator will submit any updated SAE data to Alexion within 24 hours of the date the investigational site became aware of the event.

Investigators are not obligated to actively seek AE or SAE data after conclusion of the study participation. However, if the Investigator learns of any SAE, including a death, at any time after a participant has been discharged from the study, and he/she considers the event to be reasonably related to the study intervention or study participation, the Investigator must promptly notify Alexion.

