26-week Blinded Initial Evaluation Period. The LN cohort will continue with the same treatment allocation during the 24-week Blinded Extended Treatment Period (ALXN2050 180 mg bid, ALXN2050 120 mg bid, or placebo bid). For the IgAN cohort, participants assigned to the placebo group will also be assigned to their active study treatment for the 24-week Blinded Extended Treatment Period (ALXN2050 120 mg bid or ALXN2050 180 mg bid) in a 1:1 allocation ratio at the time of initial randomization.

The randomization stratum is defined as follows:

[figure not shown]
- LN cohort: corticosteroid induction treatment initiation (prior to Screening, during Screening Period)
- IgAN cohort: mean proteinuria from 2 valid 24-hour urine collections (1 to 2 g/day, > 2 g/day)

During the OLE Period, participants in both cohorts receiving ALXN2050 during the 24-week Blinded Extended Treatment Period will continue their active treatment at the same dose level. Once an optimal dose is identified based on results of the primary analysis at Week 26 for each cohort and/or Data Monitoring Committee review of the safety and efficacy data, all participants in that cohort with at least 50 weeks of study treatment will receive the optimal dose of ALXN2050. Participants in the LN cohort randomized to the placebo group will no longer receive placebo and will continue to receive allowed concomitant therapy alone. These participants will have the option to receive ALXN2050 180 mg bid or the optimal dose (if already identified) if the participant has a renal flare or suboptimal response.

In the LN cohort, participants who meet the criteria for protocol-defined renal flare or for extrarenal systemic lupus erythematosus (SLE) flare will receive additional standard of care therapy. After Week 26, participants may also receive additional standard of care therapy for protocol-defined suboptimal response. The specific choice of additional standard of care therapy(ies) is generally at the discretion of the Investigator.

Participants who discontinue study intervention and remain on study may receive treatment consistent with local standard practice for their disease per Investigator judgment.

[figure not shown]
Figure 1: Study Design Schematic (LN Cohort)

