4.4. Exploratory Endpoint Analysis

The exploratory analyses will be based on the FAS. These analyses will be descriptive in nature and no adjustment for multiplicity will be performed. In addition, there will be no imputation for missing data or data collected on or after the receipt of additional standard-of-care therapy (LN cohort only) or treatment discontinuation unless otherwise specified.

Summary statistics will be computed and displayed by treatment group and by visit, where applicable. Descriptive statistics for continuous variables will minimally include the number of participants, mean, SD, minimum, median, and maximum. For categorical variables, frequencies and percentages will be presented.

The analyses for participants in the LN cohort and participants in the IgAN cohort will be conducted and reported separately. Participants in each disease-specific cohort will be analyzed as randomized, regardless of actual treatment received.

4.4.1. Percentage Change in Proteinuria from Baseline to Weeks 102 and 154 (Both Cohorts)

The analysis will be performed at Weeks 102 and 154 using the same approach as defined in Section 4.3.1.1. Results will be presented for each treatment sequence group.

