4.5.2. Adverse Events

The following definitions will be used for AEs:

- **Pretreatment AE:** Any AE that starts after providing informed consent, but before the first dose of study intervention (ALXN2050 or placebo)
- Treatment-emergent adverse event (TEAE): Any AE that starts between the start of the first dose of study intervention and up to 30 days after the last dose of study intervention
- Treatment-emergent serious adverse event (TESAE): A TEAE that is serious
- **Post-treatment AEs:** Any AE that starts 30 days or later after the last dose of study intervention

All AEs will be coded using MedDRA version 26.1 or higher and will be summarized by SOC and PT overall, by severity, and by relationship to treatment.

Participants having multiple AEs within a category (eg, overall, SOC, PT) will be counted once in that category. For severity/relationship tables, the participant's highest grade/most related event within a category will be counted.

TEAEs and serious adverse events (SAEs) will be summarized descriptively by treatment group. Percentages will be based on the number of treated participants in the SS within a treatment group. Tables will be sorted by descending frequency of SOC and by descending frequency of PT within an SOC.

Pretreatment and post-treatment AEs will be provided in by-participant listings and will not be included in summary tables.

In addition, AEs that occur after the receipt of additional standard of care therapy will be provided in a separate listing.

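### The LN open-label extension has no placebo-to-ALXN2050 group, and the treatment-emergent rule leaves the off-drug placebo column of the AE tables nearly empty

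*SAP*

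**What the plan says.** **Pathway.** Placebo stops at Week 50 in the LN cohort. SAP 1.2 says that these participants continue on concomitant therapy alone but "will have the option to receive ALXN2050 180 mg bid or the optimal dose (if already identified) if the participant has a renal flare"; a Suboptimal Response opens the same option. Protocol 4.1.4 and footnote c to Figure 1 agree. Protocol Table 5 (footnote a) even schedules an extra ECG for hydroxychloroquine users who start ALXN2050 this way after a Renal Flare.

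**Columns.** SAP 4.1.3 says that LN summaries for the OLE "will be presented by treatment sequence if the optimal dose is identified at Week 26". It then lists three sequences, of which "Placebo to allowed concomitant therapy only" is the only one for placebo origin. No LN layout is given for the case where no optimal dose has been identified. The IgAN paragraph of the same section has placebo-to-ALXN2050 sequences and an ALXN2050 Total column; the LN paragraph has neither.

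**Efficacy.** SAP 4.4 analyses exploratory endpoints as randomized. For Weeks 102 and 154, 4.4.1 and 4.4.2 add: "Results will be presented for each treatment sequence group".

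**Safety.** SAP Table 2 and 4.5 group safety data by treatment actually received. SAP 4.5.2 defines a treatment-emergent event as "Any AE that starts between the start of the first dose of study intervention and up to 30 days after the last dose"; doses here are those of the study drug, which that section glosses as ALXN2050 or placebo. It then states: "Pretreatment and post-treatment AEs will be provided in by-participant listings and will not be included in summary tables".

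**Collection.** Protocol 8.3.1 says "All AEs and SAEs will be collected from the signing of the ICF until the Safety Follow-up Visit", and Protocol 4.4 places that visit 30 (± 3) days after the last dose. Protocol Table 5 schedules continuous AE monitoring throughout the OLE.

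**The concern.** Protocol Table 9 gives the purpose of the extension periods as longitudinal efficacy and additional safety data. For LN, the untreated group is the only reference the OLE offers, and two rules work against it.

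First, a foreseen treatment path has no analysis group. Whoever programs the tables must choose where crossovers go, possibly after seeing the data.

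Second, the treatment-emergent window follows study drug, and off-drug participants take none. Their events after the first month of the OLE go to listings only. The ALXN2050 columns beside them may collect events for two years, and percentages are taken over treated participants with no adjustment for follow-up time. A reader comparing the columns would see a difference produced by the counting rule, even if the true event rates were equal.

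**Working it through.** **Inputs**
- Week 50 visit, D351 (Protocol Table 3); Week 154 visit, D1079, and first OLE visit, Week 63, D442 ± 14 (Protocol Table 5).
- OLE length stated as 104 weeks (Protocol 4.1.4).
- End of treatment-emergent window: last dose + 30 days (SAP 4.5.2, 6.1.7).
- LN placebo arm: 30 randomized (SAP 5).

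**1. Reproduce the plan's OLE length.** 1079 − 351 = 728 days; 728 / 7 = 104.0 weeks. This matches.

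**2. Participants who stay off drug.** The last placebo dose is at about D351, so the window closes at about 351 + 30 = D381. The earliest first OLE visit is 442 − 14 = D428, so the window has closed before any scheduled OLE visit.
- Share of OLE time covered by AE summary tables: 30 / 728 = 4.1%.
- Share sent to listings only: 698 / 728 = 95.9%. At a constant AE rate, about 96% of their OLE events would be outside the tables.
- A participant on ALXN2050 to Week 154 is covered for all 728 days, a ratio of 728 / 30 ≈ 24.

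**3. Participants who cross over.** Their last dose falls in the OLE. The single window from first dose to last dose + 30 days therefore covers their whole time up to then, including the drug-free gap. Someone starting ALXN2050 at mid-OLE (364 days after Week 50) would have 364 days without study drug, all counted as treatment-emergent.

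**4. Why the missing column matters (illustration only).** Suppose that, with no column of their own, crossovers were kept with placebo origin in the AE tables; the SAP does not direct this. Assume all 30 are followed to Week 154 and k of them cross over. Crossovers' share of the column's tabulated time is 728k / [728k + 30(30 − k)].

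| Assumed crossover | k | Share |
|---|---|---|
| 10% | 3 | 2184 / 2994 = 73% |
| 25% | 7.5 | 5460 / 6135 = 89% |
| 50% | 15 | 10920 / 11370 = 96% |

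With 25% crossing at mid-OLE, on-drug time alone is 7.5 × 364 / 6135 = 44% of what is tabulated. A minority would dominate the column.

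**5. Efficacy, by reading.** As-randomized analysis plus presentation by sequence leaves a crossover one possible group, the one labelled as concomitant therapy only. Starting ALXN2050 is not among the intercurrent events in SAP Table 6. A Renal Flare leads to additional standard of care, which is an intercurrent event, and the 4.3.1.1 method reused for Weeks 102 and 154 sets later data to missing. After a Suboptimal Response that therapy is optional (Protocol 6.5.4, 8.1.8), so a crossover by that route may trigger no intercurrent event and stay in the summary.

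**The case against.** A reader might infer more than the documents support, and several replies are sound.

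- *Drug events are hidden in the untreated comparator.* Not supported. SAP Table 2 and 4.5 require actual treatment received, so the SAP does not place on-drug events in the untreated column; it names no column for them. Table specifications are also held in a separate Data Presentation Plan that is not available here and may settle the layout.
- *Events are lost.* No. Post-treatment AEs appear in by-participant listings, and events after additional standard of care have a further listing. On-study deaths are counted with no stated treatment-emergent restriction, and laboratory data are summarised by visit. The gap concerns the AE summary tables.
- *The OLE efficacy results are wrong.* Too strong. They are exploratory and descriptive, and grouping by randomized origin is legitimate. Some post-flare data may not enter the model at all, although SAP 4.4, which says no imputation, leaves this unclear. The fault is the label.
- *Seven or more of 30 will cross over.* Protocol 2.2.3 gives Renal Flare within 1 year in up to 25% of patients, which is a ceiling; 0.25 × 30 = 7.5 is not a minimum. Dropout and the dosing pause of 06 Sep 2024 would reduce the number. Protocol 4.1.4 also makes OLE entry conditional on no Treatment Failure, a condition the synopsis omits.
- *Efficacy should be censored at crossover.* Crossover follows a flare or poor response, so censoring is informative and would flatter the untreated group. It should not be mandatory.
- *Protocol 8.3.1 stops AE collection early.* Only if read literally. Protocol 4.1 puts the 30-day follow-up after OLE completion or withdrawal, and Table 5 is explicit. The wording needs reconciling.

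What remains is that the missing sequence and the treatment-emergent rule are both in the text, and no other passage of the SAP resolves them.

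**Conclusion.** The point holds for LN reporting in the OLE. The SAP allows a path from placebo to ALXN2050 and defines no group for it: in efficacy the only available label is inaccurate, and in safety the column is undefined. Applying the written treatment-emergent rule gives off-drug LN placebo participants tabulated AE coverage of about 4.1% of the OLE, against up to 100% for ALXN2050 participants, while a crossover's drug-free time is counted as treatment-emergent.

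The 4.1% assumes a last placebo dose at about D351 and follow-up to Week 154; it is a share of time, and becomes a share of events only at a constant AE rate. The number of crossovers is unknown, so the size of any distortion cannot be given. The Week 26 primary analysis, the Week 50 analyses, alpha, power and sample size are untouched. SAP version 3.0 postdates the dosing pause and keeps the OLE analyses, so the text should be put right before they are run.

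**What to change.** 1. **SAP 4.1.3.** Add an LN sequence for placebo to ALXN2050 and an ALXN2050 Total column, as already done for IgAN. Reserve the concomitant-therapy-only label for participants who never start ALXN2050. If efficacy stays grouped by randomized origin, rename that column to say so.
2. **SAP 4.5.2 and 6.1.7.** Define an off-drug OLE observation period for LN placebo participants, from Week 50 to first ALXN2050 dose or last OLE visit, and tabulate its AEs separately. For crossovers, count treatment-emergent events on ALXN2050 only from first ALXN2050 dose to 30 days after the last.
3. **OLE AE summaries.** Add rates adjusted for exposure or follow-up, because observation time differs by column.
4. **Protocol 8.3.1.** Reconcile it with Table 5, so that AE collection for off-drug LN placebo participants clearly runs to the last OLE visit.

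The cost is SAP wording, programming and one clarifying protocol sentence. No new data are needed, since dosing dates and AEs are already scheduled for collection.

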4.1.4. Handling of Dropouts or Missing Data

No imputation will be performed for missing baseline values. For missing postbaseline data not due to IEs, no imputation will be performed.

To derive duration of disease, partial date of diagnosis will be imputed as follows:

- If day is missing, it will be imputed to the "01"
- If day and month are missing, they will be imputed to "January 01"

Partial concomitant medication start dates and AE start dates will follow the same imputation rule to derive study phase.

Missing outcome data due to the COVID-19 pandemic (eg, dropout due to COVID-19) is assumed missing-at-random (MAR).

Missing outcome data due to dosing pause is assumed MAR.

Missing data for quality-of-life (QoL) instruments will be handled as specified in the instructions for each instrument in Section 6.3.

The following may occur during the study:

- Receipt of additional standard-of-care therapy (LN cohort only)
- Treatment discontinuation (LN and IgAN cohorts)
- Dosing pause

The handling of IEs is detailed in each analysis section.

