All participants will continue to receive allowed concomitant therapy consistent with the standard of care for participants with LN and IgAN throughout the study. Participants in the LN cohort will receive additional standard of care therapy in the event of a protocol-defined Renal Flare or severe Extrarenal systemic lupus erythematosus (SLE) Flare and after Week 26, for Suboptimal Response. Approved novel treatments for LN can be used per the Investigator's discretion. However, if additional standard of care therapy is initiated, the Investigator should consult the list of disallowed medications (Section 6.5.2). If additional standard of care therapy is a prohibited medication, study intervention should be discontinued at least 3 days prior to initiation of the additional standard of care therapy.

Blinded Initial Evaluation Period

- For each disease cohort, participants will be randomly assigned in a 3:1:3 ratio on Day 1 to receive ALXN2050 180 mg twice daily (bid), ALXN2050 120 mg bid, or placebo bid throughout the Blinded Initial Evaluation Period (26 weeks).
- For the IgAN cohort, participants assigned to the placebo group on Day 1 will also be assigned to their study treatment for the Blinded Extended Treatment Period (ALXN2050 180 mg bid or ALXN2050 120 mg bid) in a 1:1 allocation ratio at the time of randomization.

Blinded Extended Treatment Period

After completion of the Blinded Initial Evaluation Period (Week 26), participants will continue to receive study intervention during a Blinded Extended Treatment Period for 24 weeks as follows:

 Participants in the LN cohort will continue to receive their randomized allocation of study intervention (ALXN2050 180 mg, ALXN2050 120 mg, or placebo) bid. After Week 26, additional standard of care therapy for participants with Suboptimal Response is allowed at the clinical discretion of the Investigator in conversation with the Medical Monitor.

- Participants in the IgAN cohort randomized to the ALXN2050 180 mg bid or ALXN2050 120 mg bid groups will continue to receive their randomized allocation of study intervention bid.
- Participants in the IgAN cohort randomized to the placebo group will receive either ALXN2050 180 mg bid (n = 12) or ALXN2050 120 mg bid (n = 12) as assigned at the time of randomization.

Open-Label Extension Period

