4.5. Safety Analyses

The safety and tolerability of ALXN2050 will be assessed based on adverse events (AEs), clinical laboratory findings, vital sign findings, electrocardiogram (ECG) abnormalities, and physical examination. All safety analyses will be performed on the SS based on the actual treatment received.

AEs will be coded in Medical Dictionary for Regulatory Activities (MedDRA) version 26.1 or higher and presented by MedDRA system organ class (SOC) and preferred term (PT).

All safety data will be provided in participant listings by treatment group. No formal hypothesis testing is planned. Safety data will be presented separately for the 26-week Blinded Initial Evaluation Period, 24-week Blinded Extended Treatment Period, and 2-year OLE Period.

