6.1.7. Adverse Events

The analysis of AEs is described in detail in Section 4.5.2.

Treatment-emergent AEs (TEAEs) are events with start dates and start times on or after the date and time of the first dose of study intervention and up to 30 days after the last dose of study intervention. If the start date of an AE is partially or completely missing and the end (stop) date and time of the AE does not indicate that it occurred prior to first dose or 30 days after the last dose, then the determination of treatment-emergent status will be based on the following:

- If the start year is after the year of the first dose of study intervention and before the year of the last dose of study intervention, then the AE is treatment-emergent; else
- If the start year is the same as the year of the first dose of study intervention and
 - the start month is missing, then the AE is treatment-emergent; else, if
 - the start month is present and is the same or after the month of the first dose of study intervention and is the same or before the last dose of study intervention, then the AE is treatment-emergent; else,
- If the start date is completely missing, then the AE is treatment-emergent.

All other AEs are considered pretreatment adverse events (PTAEs) if the start date is prior to the first dose of study intervention or post-treatment adverse events if the start date is 30 days or later after the last dose of study intervention.

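### For IgAN placebo participants who switch to ALXN2050 at Week 26, the SAP's earliest-date rule puts partly dated adverse events from the switch month in the placebo period

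*SAP*

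**What the plan says.** SAP 4.1.4 first gives a convention for deriving disease duration: a missing day in the diagnosis date becomes the 1st, and a missing day and month become 1 January. It then adds: "Partial concomitant medication start dates and AE start dates will follow the same imputation rule to derive study phase".

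Phase matters because SAP 4.5 reports safety by period, on the treatment actually received: "Safety data will be presented separately for the 26-week Blinded Initial Evaluation Period", and likewise for the two later periods. The first boundary is the Week 26 dose. SAP 4.1.1 states: "Dosing on Week 26 will be considered the start of the 24-week Blinded Extended Treatment Period". For the IgAN cohort that boundary is also a change of treatment. In SAP 4.1, "participants initially randomized to the placebo treatment group will receive ALXN2050 in the 24-week Blinded Extended Treatment Period". The Protocol synopsis plans 12 switchers to each dose, 24 in all.

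Treatment-emergent status has its own rule in SAP 6.1.7, which does not use the imputed date. For a start year equal to the first-dose year, it says that if "the start month is missing, then the AE is treatment-emergent". If the month is known and is the first-dose month or later, up to the last dose, the event is also treatment-emergent. Both hold unless the stop date shows otherwise.

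**The concern.** For disease duration, the earliest possible date costs at most a small overstatement. For phase, it resolves every ambiguity towards the earlier period. In an IgAN placebo participant the earlier period at Week 26 is placebo and the later one is ALXN2050. A partly dated event from around the first active dose can therefore be added to the placebo column and lost from the placebo-to-ALXN2050 sequence group and from the ALXN2050 Total column defined in SAP 4.1.2. That departs from the actual-treatment principle in SAP 4.5.

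A second, separate problem is that 4.1.4 and 6.1.7 can give the same event incompatible labels around the first dose. The SAP does not say which of them governs the by-period tables.

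**Working it through.** The plan states no figure on this point, so there is none to reproduce. The check applies the rule to the calendar.

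**Inputs.** The imputation rule is from SAP 4.1.4. The boundary is the Week 26 dose (SAP 4.1.1), which is Day 183 in the Protocol's Schedule of Activities, so the switch comes 182 days after first dose. The 24 planned switchers are from the Protocol synopsis. Assumption: true event days are spread evenly within the interval considered. First-dose dates run over four calendar years (1,461 days, a mean of 365.25 per year).

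**1. Switch month, day missing.** In a month of L days, with the switch equally likely on any day:

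- share of event days on or after the switch = (L + 1) / (2L); for L = 30, 31/60 = 51.7%
- share on or after the switch but imputed before it = (L − 1) / (2L); for L = 30, 29/60 = 48.3%. The only switch day that escapes is the 1st.
- ratio of the two = (L − 1) / (L + 1); for L = 30, 29/31 = 93.5%

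Over the real calendar the results are 51.6%, 48.4% and 93.6%. Errors in the other direction number 0, because the 1st is never later than the true day.

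Example: first dose 15 Jan 2024, switch 15 Jul 2024. An event recorded only as July 2024 becomes 1 Jul 2024 and is counted in the placebo period, whether it began on 3 July or 25 July.

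**2. Year-only dates of events that truly began in the extended period (Days 183 to 350).** The imputed date is 1 January of the event's year.

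- It falls in the placebo period if 1 January lies in the 182 days from first dose up to the switch: 182 / 365.25 = 49.8%.
- It falls in the correct period if 1 January lies between the switch and the event. The mean span over the 168 days is 84.5 days: 84.5 / 365.25 = 23.1%.
- Otherwise it falls before first dose: 100 − 49.8 − 23.1 = 27.1% (27.0% unrounded).

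**3. Can SAP 6.1.7 repair this?** No. It compares the partial date with the first and last dose of study intervention, and SAP 4.5.2 takes study intervention to mean ALXN2050 or placebo. A switcher's first dose is placebo, so the rule does not see the Week 26 boundary.

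**4. First-dose month, day missing.** By the same arithmetic as step 1, 93.6% of events that truly began on or after first dose get an imputed date before it. SAP 6.1.7 still classes them as treatment-emergent unless the stop date excludes it, so 0% become pretreatment events. What remains is a treatment-emergent event with a pre-dose phase.

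**5. Scale, by illustration only.** The documents give neither an event rate nor the share of partial dates. Suppose 0.5 to 1 adverse event per participant-month and 2 to 5% of dates with the day missing. Misplaced switch-month events then number:

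- low: 24 × 0.5 × 0.02 × 0.484 = 0.12
- high: 24 × 1 × 0.05 × 0.484 = 0.58

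Year-only dates would add to this. One moved participant changes an incidence by 1/12 = 8.3 percentage points in a switch group of 12, and by 1/24 = 4.2 points in the placebo arm.

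**The case against.** A reader might infer that first-dose-month events drop out as pretreatment events for all 126 participants. The SAP does not support that. Under 6.1.7 they are treatment-emergent without reference to the imputed date, and SAP 4.5.2 keeps only pretreatment and post-treatment events out of the summary tables. What is left is a conflict of labels. Table specifications sit in a separate Data Presentation Plan (SAP 1), which may settle it.

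A reader might also infer that every ambiguous event is moved away from the drug. That is not so either. At Week 26 only the 24 planned IgAN placebo participants go from placebo to ALXN2050. The other 102 (70 LN and 32 IgAN on active) keep their treatment, so a shifted event moves between two periods on the same treatment. In the first-dose month the rule acts equally on the 54 participants randomized to placebo (30 LN and 24 IgAN).

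Other points bear on size. Twenty-four is a planned number, and SAP 1 reports a pause in enrollment and dosing from 06 Sep 2024, so fewer may have switched. IgAN visits fall at Day 183 and Day 197, with continuous adverse event monitoring, which should keep partial dates near the switch few. Safety analysis is descriptive, without formal testing, and all safety data are listed by participant. These points stand. They limit the effect but do not make the rule right for switchers.

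Finally, any replacement that favours the ALXN2050 period is one-way too. That is fair, particularly for year-only dates, where an event that began months earlier on placebo could be charged to drug. It is the reason for flagging such events.

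**Conclusion.** The point holds for IgAN placebo-to-ALXN2050 participants at the Week 26 switch. There the written rule attributes ambiguous events to placebo and cannot err the other way. About 48% of day-missing dates in the switch month are misplaced if event days are even within the month. Year-only dates are exposed to the same error, and nothing in 6.1.7 corrects it.

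The first-dose-month matter is an inconsistency between two SAP rules that needs an order of precedence. It is not a loss of events.

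The overall effect is probably between a fraction of an event and a few events in descriptive tables. That rests on assumed event rates and partial-date shares and on the planned number of switchers. This is a minor point, worth correcting because the error always favours ALXN2050 and the correction is routine.

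**What to change.** In SAP 4.1.4:

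- Limit the earliest-date rule to diagnosis dates.
- State that 6.1.7 governs treatment-emergent status, and that the phase date of a treatment-emergent event cannot precede first dose.
- For IgAN placebo-to-ALXN2050 participants, when only the day is missing and the month is the switch month, set the start to the date of the first ALXN2050 dose unless the stop date is before it.
- For the same participants, assign a year-only date to the ALXN2050 period if the known parts and the stop date allow it, and flag the event in the listing.

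The sentence being replaced also covers concomitant medication start dates, so those need a phase line of their own.

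The cost is a few lines of SAP text and matching programming, with no new data. The downside is that a few events that began on placebo may be charged to ALXN2050. The flag lets a reader see which ones.
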